#### 2.4.3 Study treatment beyond RECIST progression

The number (%) of subjects who continue study treatment beyond RECIST 1.1 progression according to local investigator assessment based on protocol specified criteria will be summarized. It includes all subjects who received any study treatment (i.e., at least one dose of

any component of the study treatment) after RECIST 1.1 progression assessed by local investigator.

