### Treatment beyond disease progression

Subjects will be permitted to continue study treatment beyond disease progression per RECIST 1.1 as determined by investigator, provided they meet all the following criteria:

- Clinical benefit per investigator's judgement
- Continuation of treatment beyond initial progression will not delay an imminent intervention to prevent serious complications of disease progression
- Subject exhibits adequate tolerance to study treatment
- Subject performance status is stable
- Absence of symptoms and signs (including worsening of clinically relevant laboratory values) indicating disease progression

The reasons for the subject continuing treatment beyond progression will be documented in the eCRF.

[figure not shown]
Subjects who meet the above criteria and continue study treatment beyond initial disease progression per RECIST 1.1 will continue all study procedures as outlined in [Table 8-1b](#) and [Table 8-3](#).

In addition, subjects enrolled in Part 2, who continue study treatment beyond initial disease progression per RECIST 1.1 [REDACTED]. In case of clinical deterioration or suspicion of disease progression, a follow-up imaging assessment should be performed promptly rather than waiting for the next scheduled assessment.

[REDACTED]

[REDACTED]

[REDACTED]

Please refer to [Section 8.3](#) for additional information on RECIST 1.1 [REDACTED].

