#### 16.1.3.2.8 Definition of start and end dates for time to event variables

##### Assessment date

For each assessment (i.e. evaluation number), the **assessment date** is calculated as the latest of all measurement dates (e.g. X-ray, CT-scan) if the overall lesion response at that assessment is CR/PR/SD/UNK. Otherwise - if overall lesion response is progression - the assessment date is calculated as the earliest date of all measurement dates at that evaluation number.

In the calculation of the assessment date for time to event variables, any unscheduled assessment should be treated similarly to other evaluations.

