##### End dates

The end dates which are used to calculate ‘time to event’ variables are defined as follows:

- Date of death (during treatment as recorded on the treatment completion page or during follow-up as recorded on the study evaluation completion page or the survival follow-up page).
- Date of progression is the first assessment date at which the overall lesion response was recorded as progressive disease.
- Date of last adequate tumor assessment is the date the last tumor assessment with overall lesion response of CR, PR or SD which was made before an event or a censoring reason occurred. In this case the last tumor evaluation date at that assessment is used. If no post-baseline assessments are available (before an event or a censoring reason occurred) the date of randomization/start of treatment is used.

- Date of next scheduled assessment is the date of the last adequate tumor assessment plus the protocol specified time interval for assessments. This date may be used if back-dating is considered when the event occurred beyond the acceptable time window for the next tumor assessment as per protocol (see [Section 16.1.3.2.8](#)).

**Example** (if protocol defined schedule of assessments is 3 months): tumor assessments at baseline - 3 months - 6 months - missing - missing - PD. Date of next scheduled assessment would then correspond to 9 months.

- Date of discontinuation is the date of the end of treatment visit.
- Date of last contact is defined as the last date the patient was known to be alive. This corresponds to the latest date for either the visit date, lab sample date or tumor assessment date. If available, the last known date patient alive from the survival follow-up page is used. If no survival follow-up is available, the date of discontinuation is used as last contact date.
- Date of secondary anti-cancer therapy is defined as the start date of any additional (secondary) antineoplastic therapy or surgery.

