**Table 2-1      Last contact date data sources**

Source data	Conditions
Last contact date/last date patient was known to be alive from Survival eCRF page	Patient status is reported to be alive or unknown in the survival eCRF page
Start/End dates from further antineoplastic therapy	Non-missing medication/procedure term.
Start/End* dates from study treatment eCRF	Non-missing dose. Doses of 0 are allowed.

Source data	Conditions
End of treatment date from end of treatment page	No condition.
Tumor (RECIST) assessment date	Evaluation with a response.
Date of verification for treatment beyond RECIST 1.1 PD	Will the subject continue treatment beyond disease progression as per RECIST 1.1? marked as 'Yes'
PK collection dates	Was sample taken marked as 'Yes'.
Vital signs/ECGs/Laboratory date	At least one non-missing parameter value
Performance Status date	Non-missing performance status
Start/End dates of AE	Non-missing verbatim term

The last contact date is defined as the latest complete date from the above list on or before the data cut-off date. The cut-off date will not be used for last contact date unless the patient was seen or contacted on that date. No date post cut-off date will be used. Completely imputed dates (e.g., the analysis cut-off date programmatically imputed to replace the missing end date of a dose administration record) will not be used to derive the last contact date. Partial date imputation is allowed for event (death)/censoring is coming from 'Survival information' eCRF.

The last contact date will be used for censoring of patients in the analysis of time to event endpoints.

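### SAP 2.4.3 contradicts itself on who counts as treated beyond RECIST progression: its counting rule takes in subjects with a single post-progression dose and no decision to continue

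*SAP*

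**What the plan says.** SAP 2.4.3 has two sentences. The first describes the summary as the number and percentage of "subjects who continue study treatment beyond RECIST 1.1 progression according to local investigator assessment based on protocol specified criteria". Those criteria are in Protocol 6.1.4: five conditions, all of which must be met. The protocol adds that "The reasons for the subject continuing treatment beyond progression will be documented in the eCRF".

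The second sentence supplies the counting rule. It opens "It includes all subjects who received any study treatment (i.e., at least one dose of". The rest of that sentence fixes which dose qualifies and when: "any component of the study treatment) after RECIST 1.1 progression assessed by local investigator".

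Two other places bear on how the rule would be programmed:

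- **Progression date.** Protocol Appendix 1 (16.1.3.2.8, End dates) states: "Date of progression is the first assessment date at which the overall lesion response was recorded as progressive disease". For the assessment date itself: "if overall lesion response is progression - the assessment date is calculated as the earliest date of all measurement dates at that evaluation number".
- **The recorded decision.** SAP Table 2-1 lists a verification date for treatment beyond RECIST 1.1 progression, on the condition "Will the subject continue treatment beyond disease progression as per RECIST 1.1? marked as 'Yes". The SAP uses this item only as a source for the last contact date.

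**The concern.** The two sentences describe different groups. The first is the group kept on treatment after the investigator judged that the protocol conditions were met. The second is everyone with at least one recorded dose after progression. Only the second can be programmed as it stands, so it is likely to be the one used.

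Protocol 9.1.1 makes progression a reason for mandatory discontinuation, with continuation as the exception. A table on treatment beyond progression should tell the reader how often that exception was used. If it also takes in subjects who swallowed a few tablets between the scan and the decision to stop, the clinical study report overstates deliberate continuation, and the reader cannot separate the two groups from the table.

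**Working it through.** The plan states no figure for this summary, so there is none to reproduce. The check sets the passages side by side and then asks how far the count could move.

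**Step 1: who satisfies each sentence.** Take a subject whose scan shows progression, who takes capmatinib until the scan has been read and the investigator decides to stop, and then stops.

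- First sentence: not counted, because there was no decision to continue under Protocol 6.1.4.
- Second sentence: counted if any dose falls after the progression date.

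**Step 2: the anchor date.** SAP 2.4.3 names none. The only progression date that the documents define is the one in Appendix 1, the earliest measurement date of the evaluation. That date precedes the decision whenever the scan is read on a later day.

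**Step 3: doses in the gap.** Capmatinib is taken continuously twice daily (Protocol 6.7.2.1). For a lag of L days from scan date to stop, the doses dated after the scan number up to 2 × L:

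- L = 1 day: up to 2 doses
- L = 7 days: up to 14 doses

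One dose is enough to be counted.

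**Step 4: the period before amendment 01.** Protocol 8.3.1.3 preferred that subjects stay on treatment while awaiting the expedited central read, which was due within 5 business days of image receipt. If the central read did not find progression, the subject was to continue unless there was a medical need to change. Such a subject has investigator-assessed progression and later doses, without Protocol 6.1.4 being the basis for continuing. The section lapsed with amendment 01 (13-Oct-2021). By 06-Sep-2021, 19 patients were still on capmatinib. If all 31 treated patients had started by then, 31 − 19 = 12 had stopped before the amendment; the reasons are not given.

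**Step 5: size, under stated assumptions.** Among progressors with no decision to continue:

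share counted = (share dosing at the scan) × (share stopping at least 1 day after the scan date)

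Neither share is in the documents. Assume 70–100% for the first and 50–100% for the second:

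- low end: 0.70 × 0.50 = 35%
- high end: 1.00 × 1.00 = 100%

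The share reaches 90% only near the top of both ranges, for example 1.00 × 0.90 or 0.90 × 1.00.

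As a second illustration, assume that all are dosing at the scan and that the lag is exponential with mean m days. The share with a lag of at least 1 day is exp(−1/m): 61% at m = 2 and 87% at m = 7. A 14-day minimum gap, exp(−14/m), would cut this to between 0.1% and 13.5%.

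**Step 6: what the table would show.** SAP 2.4.1 uses the safety set for study-treatment summaries. It is identical to the FAS (SAP 2.2), and Protocol 4.1 gives 31 treated. Suppose, purely for illustration, that 10 progress on treatment and 2 have a recorded decision to continue and are dosed afterwards:

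- count of decisions: 2/31 = 6.5%
- second-sentence count, low end: 2 + 0.35 × 8 = 4.8, and 4.8/31 = 15.5%
- second-sentence count, high end: 2 + 8 = 10, and 10/31 = 32.3%

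**Step 7: endpoints.** Appendix 1 (16.1.3.1) excludes assessments after progression from best overall response, so ORR and DCR do not move. PFS ends at first documented progression (SAP 2.7.1).

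**The case against.** The strongest reply is that the first sentence governs and the second only clarifies that any component counts, so that capmatinib alone qualifies. The clarification has a purpose: SAP 2.1.1.1 defines study treatment as both drugs, and spartalizumab had been stopped. But the second sentence says that all subjects with such a dose are included, and does not refer back to the criteria. If only a clarification was meant, the text needs to say so.

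The scan-date anchor is also an inference. The Appendix 1 rule is written for time-to-event variables, and SAP 2.4.3 does not cite it. If the sponsor means the day on which the investigator assessed progression, most of the over-count could go. This stands, and it is a reason to state the date.

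The dataset specifications and table shells, which are separate documents, may already use the eCRF item. That cannot be checked here; the SAP text does not use it.

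Finally, counting actual exposure after progression is a legitimate description, and a count based only on the eCRF answer would miss subjects dosed well past progression with no recorded Yes. This also stands, so the dose-based count should be kept as its own line.

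In the other direction, a reader might infer that nearly every on-treatment progressor will be counted. The documents do not support that: they give neither the scan-to-stop lag nor the share dosing at the scan, and subjects who are interrupted or stop on the scan day would not be counted.

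**Conclusion.** The inconsistency within SAP 2.4.3 is on the page and needs no assumption. The inflation of the count is conditional: it requires programming from the second sentence and dating progression to the scan. On those terms the error is upward, and many on-treatment progressors, possibly most, would be counted without a decision to continue. The range of 35% to 100% rests on assumed inputs and should not be read as an estimate.

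The consequence is limited to one descriptive table. Nor should a reader infer any bias in the efficacy results. Subject-level dose listings are planned (SAP 2.4.1), so the count could be checked by hand, but the table would still mislead. The change is worth making before database lock because the decision item appears to be collected already.

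**What to change.** Replace the second sentence of SAP 2.4.3 with two defined lines, both with the safety set (31 treated) as denominator:

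1. **Headline count:** subjects whose eCRF item on continuing treatment beyond RECIST 1.1 progression is answered Yes and who have at least one non-zero dose of either drug after the verification date.
2. **Separate line, labelled as such:** subjects with any non-zero dose after the progression date but no recorded Yes. State the progression date used, for example the Appendix 1 date.

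With the illustrative figures above, the first line would read 2/31. The second would hold at most 8/31, instead of the two groups being merged.

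The cost is one extra derivation and one extra table line. The downside is that the headline count relies on the eCRF item being completed, and on the verification date standing for the decision, which the SAP does not spell out. The second line shows how many subjects an incomplete item could affect.

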#### **2.4.4 Prior, concomitant and post therapies**

Summaries and listings described in this section will be based on the FAS.

##### **2.4.4.1 Prior anti-neoplastic therapies**

The number (%) of subjects who received any prior anti-neoplastic medication, radiotherapy or surgery will be summarized.

The summary of prior anti-neoplastic medications will include the total number of regimens (note: there can be more than one medication per regimen), therapy type at last treatment, setting at last treatment. Prior antineoplastic medications will also be summarized by Anatomical Therapeutic Chemical (ATC) class, and preferred term.

The summary of prior anti-neoplastic radiotherapy will include the radiotherapy locations, (including all locations recorded for each subject), setting at last radiotherapy, and best response at last radiotherapy.

The summary of prior anti-neoplastic surgery will include the time (in months) between the last surgery (non-biopsy procedure) to start of study treatment, procedure at last surgery and residual disease at last surgery.

All prior anti-neoplastic medication, radiotherapy and surgery will be listed.

Imputation rules for partially missing dates are provided in [Section 5.1.3.1](#).

##### **2.4.4.2 Post treatment anti-neoplastic therapy**

Anti-neoplastic therapies (medications, radiotherapies and surgeries) since discontinuation of study treatment will be listed.

##### **2.4.4.3 Concomitant therapies**

Concomitant therapy is defined as all interventions (therapeutic treatments and procedures) other than the study treatment administered to a patient coinciding with the study treatment period. Concomitant therapy includes medications (other than study drugs) starting on or after the start date of study treatment or medications starting prior to the start date of study treatment and continuing after the start date of study treatment.

Concomitant medications will be coded using the World Health Organization (WHO) Drug Reference Listing (DRL) dictionary that employs the WHO Anatomical Therapeutic Chemical (ATC) classification system and summarized by lowest ATC class and preferred term using frequency counts and percentages. Surgical and medical procedures will be coded using MedDRA and summarized by SOC and preferred term. Concomitant medications with immunosuppressive intent will be summarized by lowest ATC class and preferred term using frequency counts and percentages. These summaries will include:

1. Medications starting on or after the start of study treatment but no later than 30 days after last dose of study treatment and

2. Medications starting prior to start of study treatment and continuing after the start of study treatment.

Listings will be provided to report medications starting between 30 days after last dose of study treatment and 150 days after last dose of spartalizumab.

## 2.5 Analysis of the primary objective

The primary objective is to evaluate the anti-tumor activity of capmatinib in combination with spartalizumab, as measured by overall response rate (ORR) by investigator assessment according to RECIST 1.1 (see [\[Appendix 16.1.1-Protocol-Section 16.1\]](#)).

### 2.5.1 Primary endpoint / estimand

Overall response rate (ORR) is defined as the proportion of subjects with confirmed best overall response (BOR) of complete response (CR) or partial response (PR) according to RECIST 1.1 (see [\[Appendix 16.1.1-Protocol-Section 16.1\]](#)). ORR will be calculated based on the FAS.

Subjects with only non-measurable disease at baseline will be part of the analysis and will be included in the numerator only if a complete response was observed.

### 2.5.2 Statistical hypothesis, model, and method of analysis

Overall response rate (ORR) by investigator assessment is calculated based on the data from the FAS and the corresponding 95% CI based on the exact binomial distribution ([Clopper and Pearson 1934](#)) will be presented.

Participants who had never received one of the investigational drugs will be excluded from the efficacy analysis.

### 2.5.3 Handling of intercurrent events for the primary estimand

The primary estimand will account for the different intercurrent events as follows:

- Discontinuation of spartalizumab for any reason:** BOR will take into account all available tumor assessments irrespective of spartalizumab discontinuation reasons.
- Discontinuation of tumor assessment follow up with approval of protocol amendment:** BOR will take into account all available tumor assessments up to the last valid tumor assessment prior to approval of protocol version 01.
- Any public health emergency as declared by local or regional authorities, e.g., pandemic, epidemic or natural disaster:** BOR will take into account all tumor assessments irrespective of any public health emergency.
- New anti-neoplastic therapy:** Tumor assessment data collected after starting new anti-neoplastic therapy will be excluded from the BOR derivation.

